10.1	OPA-15406 Plasma Concentrations	24
10.2	Handling of Data	25
11	Pharmacodynamic Analysis	20
12	Pharmacogenomic Analysis	20
13	Interim Analysis	20
14	Changes from Planned Analysis Pl	an27

Clinic	cal Study Report 271-102-00016	16.1.9 Documentation of Statistical Methods
Proto	col 271-102-00016	
15	References	27
16	Amendment History	27

List of Appendices

Appendix 1	Criteria for Potential Hy's Law	31
Appendix 2	List of Tables and Figures	32
Appendix 3	List of Subject Data Listings	50

List of Abbreviations and Definition of Terms

Abbreviation	Definition
ALT (GPT)	Alanine aminotransferase
AST (GOT)	Aspartate aminotransferase
BSA	Body surface area
CTCAE	Common terminology criteria for adverse events
EASI	Eczema Area and Severity Index
IGA	Investigator's Global Assessment
MedDRA	Medical Dictionary for Regulatory Activities ICH
OC	Observed cases
POEM	Patient-Oriented Eczema Measure
TEAE	Treatment-emergent adverse event

1 Introduction

The purpose of this statistical analysis plan (SAP) is to describe the detailed analysis methods of the planned statistical analyses to be included in the Clinical Study Report (CSR) for Trial 271-102-00016.

2 Trial Objectives

The objectives and endpoints of the trial are shown below.

Table 2-1 Trial Objectives and Endpoints		
Objectives	Endpoints	
Primary objective: To investigate the efficacy of 0.3% OPA-15406 ointment when administered twice daily for 4 weeks in infants younger than 2 years of age with AD	Efficacy endpoint: Success rate in Investigator's Global Assessment (IGA) (Percentage of subjects with an IGA score of 0 or 1 with improvement by at least 2 grades)	
Secondary objectives: This trial will be conducted in infants younger than 2 years of age with AD To investigate the safety of 0.3% OPA-15406 ointment when administered twice daily for 4 weeks To investigate the efficacy and safety of 0.3% or 1% OPA-15406 ointment when administered twice daily for 52 weeks To investigate the pharmacokinetics of 0.3% or 1% OPA-15406 ointment when administered twice daily for 4 weeks	 Efficacy endpoints: Response rate in Eczema Area and Severity Index (EASI) 90 (improvement of ≥90% in EASI), EASI 75 (improvement of ≥75% in EASI) and EASI 50 (improvement of ≥50% in EASI) Change from baseline in IGA score Percent change from baseline in the total score of EASI and each clinical sign score Change from baseline in the total score of Patient-Oriented Eczema Measure (POEM) Change from baseline in the total affected body surface area (BSA) (%) Safety endpoints: Adverse events (AEs) Vital signs, body weight Clinical laboratory tests Pharmacokinetic endpoint: Plasma concentration of OPA-15406 	

3 Trial Design

3.1 Type/Design of Trial

This trial is a phase 3, multicenter, open-label, uncontrolled trial to evaluate the efficacy and safety of OPA-15406 ointment in infants younger than 2 years of age with atopic dermatitis.

1) Screening period

After obtaining informed consent from the subject's legal guardian, the investigator or subinvestigator will perform the screening examination. The screening period is defined as the period between the day of screening examination and the day of baseline examination (2 - 30 days).

2) IMP administration period

The IMP administration period is defined as the period between the day of baseline examination and the end of Week 52 examination (or the end of withdrawal examination). The primary assessment part is defined as the period between the baseline examination and the Week 4 examination, and the long-term extension part is defined as the period between the Week 4 examination and the Week 52 examination. Subjects who meet the inclusion and exclusion criteria at the baseline examination will be prescribed with the IMP. The IMP will be administered to the treatment area from the day of baseline examination twice daily for 52 weeks. If a subject discontinues the IMP administration between the day of baseline examination and the day of Week 52 examination, a withdrawal examination will be performed for that subject.

3) Trial period

The trial period for individual subjects is the period from the day of obtaining the written informed consent from the subject's legal guardian to the day of the Week 52 examination (or withdrawal examination). For subjects who missed the Week 52 examination (or withdrawal examination), the day of discontinuation will be the day when the investigator or subinvestigator determined that the subject was to be withdrawn from the trial. It does not include the follow-up period for AEs.

	Screening period (2 - 30 days)	IMP administration period (52 weeks)			IMF		
		OPA-15	assessment 0.3% 5406 ointm vice daily			[Long-term extension part] ^a 0.3% or 1% OPA-15406 ointment Twice daily	
Informed consent	Baseline examination	Week 1 examination	Week 2 examination	Week 4 examination	 •		Week 52 examination

a Long-term extension part (Week 4 - 52 examination)

- Subjects are scheduled to visit every 4 weeks, and the use of 1% formulation is also acceptable in accordance with dose increase criteria.
- Subjects whose dose is increased to 1% formulation for the first time are scheduled to visit 2 weeks after the start of 1% formulation administration.

Figure 3-1 Trial Design Schematic

3.2 Dosing Methods

3.2.1 Dose, Regimen, and Treatment Period

As the starting dose, 0.3% formulation will be administered twice daily (approximately 12 hours apart between morning and night administrations) for 52 weeks.

Primary Assessment Part (Baseline Through Week 4 Examination)

- The 0.3% formulation will be administered twice daily for 4 weeks.
- Even when the affected area is relieved, IMP administration should be continued there as the treatment area.

Long-term Extension Part (Week 4 Examination through Week 52 Examination)

- If subjects meet the dose increase criteria (see Section 3.2.2.1) at each 4-weekly assessment visit following the Week 4 examination, the 1% formulation will be used.
- When subjects show an improvement in skin symptoms and use of the 1% formulation is considered unnecessary, the dosage can be reduced to the 0.3% formulation. As a general rule, formulation switching should be done after the 4-weekly assessment (the formulation may be switched before the 4-weekly assessment if prompt dose reduction is required due to AEs or for other reasons).
- If all skin symptoms have resolved, IMP administration may be suspended based on the judgment of the physician. If skin symptoms relapse after interruption, IMP administration will be restarted.

The amount of IMP (g) per dose is 10 g/m² BSA, which is calculated as follows.

1) The subject's BSA (m²) will be calculated based on height and body weight at each examination, using the following equation.

BSA (m²) =
$$\sqrt{\frac{\text{Ht (cm)} \times \text{Wt (kg)}}{3600}}$$

BSA = body surface area; Ht = height; Wt = body weight

- 2) The treatment area will be specified.
- 3) The amount of IMP (g) per dose will be calculated as "subject's BSA (m²)" × "treatment area (%)" × "10 g/m²." Example: In case of a BSA of 0.7 m² and an affected BSA of 32%: 0.7 m² × 0.32 × 10 g/m² = 2.24 g

The method of IMP administration is specified in the separate procedure for IMP administration

3.2.2 Dose Modification of the Investigational Medicinal Product

3.2.2.1 Dose Increase

For subjects receiving the 0.3% formulation with an IGA score of 2 or greater, the dose will be increased to the 1% formulation unless a concern about unacceptable tolerability is identified at a 4-weekly assessment (in the long-term extension part) including the Week 4 examination. Even for subjects with an IGA score of less than 2, the dose can be increased if judged necessary by the investigator or subinvestigator. Dose increase will be recorded together with the reason in the source documents and eCRF.

3.2.2.2 Dose Reduction

For subjects receiving the 1% formulation, the dose can be reduced to the 0.3% formulation if judged necessary by the investigator or subinvestigator (eg, improvement in skin symptoms, occurrence of an AE) at a 4-weekly assessment after the Week 4 examination (in the long-term extension part). Dose reduction will be recorded together with the reason in the source documents and eCRF.

3.2.2.3 Interruption (Treatment Interruption)

IMP administration must not be suspended until the Week 4 examination. Interruption will be allowed if judged necessary by the investigator or subinvestigator (eg, resolution of skin symptoms, exacerbation of skin symptoms [which requires rescue medication], occurrence of an AE [excluding exacerbation of skin symptoms]) at a 4-weekly

assessment after the Week 4 examination (in the long-term extension part). Interruption will be recorded together with the reason in the source documents and eCRF. The investigator or subinvestigator should perform the specified examination/assessments during interruption, and decide on the necessity of restarting IMP administration.

3.2.2.4 Restarting IMP Administration After Interruption

Following interruption, restarting IMP administration (exacerbation of skin symptoms, improvement of skin symptoms [in cases where IMP administration was suspended to allow rescue medication], improvement of an AE [excluding exacerbation of skin symptoms]) will be recorded together with the reason in the source documents and eCRF.

3.3 Trial Population

Infants 3 months or older and younger than 2 years of age with AD and an IGA score of 2 or 3.

3.4 Handling of Time Points

The number of days from IMP administration to the endpoint measurement day will be calculated with the start day of IMP administration set as the starting point (Day 1). In determining the assessment time points for analyses, unscheduled data and withdrawal data, as well as scheduled visit data, will be included. However, unscheduled data obtained at 2 weeks after the start of 1% formulation administration and between 4 and 8 weeks after the scheduled visit will be excluded from the determination of assessment time points in analysis. The acceptable windows for time points in the analysis of safety and efficacy endpoints will be as shown in Table 3.4-1. When there are multiple non-missing measurement values in the acceptable window, the last data in the acceptable window will be adopted. Regarding efficacy and safety endpoints, the latest data among all the data obtained after the start of IMP administration will be adopted as the last time (Last Visit).

The data nearest to the start day of IMP administration among predose data including screening data will be adopted as the baseline for analysis.

Table 3.4-1	Acceptable Windows for Time Points in Analysis				
Week	Trial Day	Interval			
Baseline		1			
Week 1	2	10			
Week 2	11	21			
Week 4	22	42			
Week 8	43	70			
Week 12	71	98			
Week 16	99	126			

Table 3.4-1	Acceptable Windows for Time	Points in Analysis
Week	Trial Da	y Interval
Week 20	127	154
Week 24	155	182
Week 28	183	210
Week 32	211	238
Week 36	239	266
Week 40	267	294
Week 44	295	322
Week 48	323	350
Week 52	351	372

For subjects receiving the 1% formulation, analysis time points with starting point of dose increase to the 1% formulation will also be defined in addition to the above-described time points in analysis. For instance, when the dose is increased to 1% at Week 4, the record corresponding to Week 4 will be defined as that at the time of increase to 1%, and Week 2 After Dose Increase will be defined as the time point specified in the CRF (2 weeks after the start of 1% formulation administration). Week 4 After Dose Increase and later are defined as shown in Table 3.4-2.

A	nalysis Sta	Windows for Time Points in arting From the Time of Dose
In	crease	
Week		Definition of time points
Time of increase to 1%		The time point on the same day as the day that the doctor first directed a dose increase
Week 2 After Dose Increase		2 weeks after the start of 1% formulation administration (the time point specified in the CRF)
Week 4 After Dose Increase		Analysis visits specified in Table 3.4-1 minus
Week 8 After Dose Increase		Week at increase to 1%
Week 12 After Dose Increase		
Week 16 After Dose Increase		
Week 20 After Dose Increase		
Week 24 After Dose Increase		
Week 28 After Dose Increase		
Week 32 After Dose Increase		
Week 36 After Dose Increase		
Week 40 After Dose Increase		
Week 44 After Dose Increase		
Week 48 After Dose Increase		

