3.5.1 IGA Response

Response (improvement) is defined as an IGA score, which is the primary endpoint, of 0 or 1 with improvement of at least 2 grades from baseline. Subjects without the above improvement will be handled as non-responders. In addition, subjects with missing IGA data will be handled as non-responders.

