5.4 Handling of Missing Data

Missing data are not imputed. For IGA response, EASI 75, EASI 90, and EASI 50, subjects with missing IGA or EASI scores are handled as non-responders.

6 Primary and Secondary Endpoints

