8.2 Key Secondary Efficacy Endpoint Analyses

In the same manner as the primary endpoint analysis in 8.1, the number of subjects with an IGA response and success rate at each assessment time point and their two-sided 95% confidence intervals (Clopper-Pearson method) will be calculated for each treatment group and all subjects.

By using OC data, the number of subjects with an IGA response and success rate at each assessment time point and the last time (Last Visit) and their two-sided 95% confidence intervals (Clopper-Pearson method) will be calculated for each treatment group and all subjects. The success rate at each assessment time point will be graphically shown.

The cumulative number and rate of subjects who improved at least once by each assessment time point with IGA response and their two-sided 95% confidence intervals (Clopper-Pearson method) will be calculated by treatment group and for all subjects. The success rate at each assessment time point will be graphically shown.

EASI 75, EASI 90, and EASI 50 will be analyzed in the same manner as IGA response.

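### The Week 52 analysis window closes at Day 372 with no later visit competing for the data, so an observed late final examination can count as Week 52 non-response

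*Combined protocol and SAP*

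**What the plan says.** Section 3.4 assigns data to visits by trial day, counted "with the start day of IMP administration set as the starting point (Day 1"). On the limits it says: "The acceptable windows for time points in the analysis of safety and efficacy endpoints will be as shown in Table 3.4-1". The last two rows of that table read "Week 48 323 350" and "Week 52 351 372". There is no row after Week 52. Where a window holds several values, the last is used. Separately, the latest of all data after the start of treatment is used as Last Visit, with no window limit.

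Section 3.5.1 adds that "subjects with missing IGA data will be handled as non-responders", and section 5.4 repeats this for both scales: "subjects with missing IGA or EASI scores are handled as non-responders". Section 8.2 carries the rule to every visit ("In the same manner as the primary endpoint analysis in 8.1, the number of subjects with an IGA response and success rate at each assessment"), and EASI 50/75/90 follow. Section 8.4 also calls for Week 52 results by age, under both the non-responder and the observed-case (OC) approach.

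On scheduling, section 3.1 says of the extension part: "Subjects are scheduled to visit every 4 weeks". It ends the IMP administration period at the Week 52 (or withdrawal) examination, not on a fixed day.

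**The concern.** From Week 4 to Week 48 a visit up to 13 days late keeps its place in the by-visit analysis. At Week 52 an examination more than 7 days late does not, although no following visit could claim the record. The subject attended and was scored, but the Week 52 responder analysis treats the score as missing and so as a failure.

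Efficacy and safety over 52 weeks are a stated secondary objective, and Week 52 is its end point. The same windows govern safety endpoints, so the Week 52 laboratory and vital-sign summaries (sections 9.3 and 9.4) lose the record too. Table 3.4-2 derives its time points from Table 3.4-1, so for a subject increased to 1% at Week 4 the cut carries over to Week 48 After Dose Increase (52 - 4 = 48).

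**Working it through.** **Inputs.** Window limits are from Table 3.4-1. Treatment starts on Day 1 (section 3.4). The SAP prints no nominal visit days; I take Week k as Day 7k + 1. Missing-data rules are from sections 3.5.1 and 5.4.

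**Step 1: offsets (limit minus nominal day).**

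| Week | Window (days) | Nominal 7k + 1 | Offsets | Length (days) |
|---|---|---|---|---|
| 4 | 22-42 | 29 | -7 / +13 | 21 |
| 8 | 43-70 | 57 | -14 / +13 | 28 |
| 48 | 323-350 | 337 | -14 / +13 | 28 |
| 52 | 351-372 | 365 | -14 / +7 | 22 |

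Weeks 12 to 44 have the same offsets as Week 8. An upper limit of +13 at Week 52 would be 365 + 13 = Day 378, so the shortfall is 378 - 372 = 6 days (Days 373-378). If nominal is taken as 7k, the upper offsets become +14 and +8, and the shortfall is still 6 days.

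**Step 2: a Week 52 examination on Day 375, with no other value in Days 351-372.**
- Week 52 responder rates: no value in the window, so missing, so non-response.
- Week 52 OC and other by-visit summaries: the subject drops out.
- Cumulative response: an earlier response still counts.
- Last Visit: the Day 375 value is used.

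**Step 3: a Week 48 visit that slips to Day 351.**
- If the true Week 52 examination is on Days 352-372, both values are in the window and the last-value rule picks the true one. Nothing is lost.
- If the true Week 52 examination is after Day 372, the Week 48 value is reported as Week 52. A visit 28 days after Day 351 falls on Day 379, so even a limit of Day 378 would miss it. Here the error can go in either direction, because an actual but earlier score is used.

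**Step 4: size for the Step 2 case.** Drop in the Week 52 success rate = late share x success rate. The late share is the proportion of analysed subjects with no value in the window and a final value after Day 372. Neither factor is in the documents; both are assumed, with lateness taken as unrelated to response.

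| Late share | Success rate 50% | Success rate 70% |
|---|---|---|
| 2% | 1.0 points | 1.4 points |
| 5% | 2.5 points | 3.5 points |
| 10% | 5.0 points | 7.0 points |

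Each affected responder lowers the rate by 1/N: 3.3 points at N = 30, 2.5 at N = 40 and 1.7 at N = 60 (N is assumed, as the published text shows none). At N = 40 with 24 responders, the rate is 24/40 = 60.0% (Clopper-Pearson 95% CI 43.3-75.1). If 3 of them are seen only after Day 372, it is 21/40 = 52.5% (36.1-68.5).

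**The case against.** The strongest reply is that the different limit is not an inconsistency. The windows from Week 4 to Week 48 are contiguous, and each ends the day before the next begins. Their +13 is a by-product of that layout, not a judgement that 13 days of lateness is acceptable. The last window has no successor, so its end has to be chosen, and +7 is an ordinary choice. Weeks 1 and 2 end at +2 and +6, so the table is not uniform anyway. This stands: a reader might infer a drafting error from the uneven offsets, and the documents do not support that. It does not show a benefit from the cut. The SAP gives no reason for it, and because section 3.1 ends the IMP administration period at the examination itself, a later limit brings in no post-treatment data.

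Other stronger readings also fail:
- That late data are thrown away altogether. They remain in Last Visit, which sections 8.2 to 8.4 analyse for response, scores, shifts and subgroups. Last Visit does mix completers with early withdrawals, so it does not replace the Week 52 rate.
- That any slipped Week 48 visit displaces the real Week 52 value. The last-value rule prevents this unless the Week 52 examination is itself after Day 372.
- That delays must accumulate over the year. The SAP does not say that each visit is timed from the one before.

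The size is also open. If the protocol's visit tolerance is 7 days or less, only out-of-tolerance visits are affected. The planned efficacy output consists of descriptive rates with confidence intervals in an open-label, uncontrolled trial, and for the missing-value case the error is conservative.

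**Conclusion.** The point holds as a minor improvement to the Week 52 by-visit results. The 6-day shortfall against the earlier windows is exact. It follows from the SAP's own rules that an observed final examination after Day 372, with nothing else in Days 351-372, is scored as Week 52 non-response. The effect on the success rate is then downward. It is about 1 to 3.5 points for assumed late shares of 2-5% and success rates of 50-70%, and possibly near zero, depending on a visit tolerance that is not shown. Nothing in the documents supports a late share as high as 10%; that row only shows how the loss scales.

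A reader might infer that the trial's main result is at risk. It is not: the primary endpoint is at Week 4, whose window is not involved.

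**What to change.** In Table 3.4-1, leave the Week 52 window open-ended from Day 351 through the end of the IMP administration period (the Week 52 or withdrawal examination). Keep the existing last-value rule, and flag any value after Day 372 in the listings. This stays day-based at its lower end and covers the slipped Week 48 case in Step 3. Extending only to Day 378 is a partial alternative that matches the earlier +13 but misses that case.

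If Day 372 is kept, state the reason and add a sensitivity analysis that uses final-visit values after it.

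The cost is one table entry and a flag. The downside is that a few assessments later than nominal enter Week 52.

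### A withdrawal examination held after the Week 4 examination and by Day 42 replaces the Week 4 IGA in the primary analysis, even if the infant has already started 1%

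*Combined protocol and SAP*

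**What the plan says.** SAP section 3.4 lists the data used to fill the analysis time points: "unscheduled data and withdrawal data, as well as scheduled visit data, will be included". It then excludes certain unscheduled data, namely those obtained 2 weeks after 1% is started and those in a loosely described 4-to-8-week interval. Withdrawal data are not part of that exclusion. Table 3.4-1 sets the Week 4 window at Day 22 to Day 42. The rule for choosing among several values is: "When there are multiple non-missing measurement values in the acceptable window, the last data in the acceptable window will be adopted".

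Section 3.1 requires a withdrawal examination for any infant who stops treatment between baseline and Week 52: "a withdrawal examination will be performed for that subject". Section 8 uses data at the Table 3.4-1 time points whichever formulation the infant is on, and during interruption, unless otherwise noted. Section 8.1 names the IGA success rate at Week 4 as the primary endpoint and gives no separate rule for selecting that value.

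The objective in Table 2-1 is "To investigate the efficacy of 0.3% OPA-15406 ointment when administered twice daily for 4 weeks". Section 3.1 sets the matching period: "The primary assessment part is defined as the period between the baseline examination and the Week 4 examination". Section 3.2.2.1 provides for a dose increase from the Week 4 examination onward, unless tolerability is a concern: "For subjects receiving the 0.3% formulation with an IGA score of 2 or greater, the dose will be increased to the 1% formulation".

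**The concern.** The primary result should describe infants after 4 weeks of 0.3%. Under the stated rule, an observed Week 4 examination can be displaced by an examination held up to two weeks later, after the primary assessment part has ended and possibly on the other concentration.

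Take an infant with baseline IGA 3 and IGA 2 at a Week 4 examination on Day 29. This is a non-responder, whom section 3.2.2.1 moves to 1%. If the infant withdraws on Day 40 with IGA 1, the rule selects Day 40 and the infant counts as a Week 4 responder for 0.3%.

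The same selection feeds the Week 4 EASI responses, which section 8.2 analyses in the same way as IGA response. It also feeds the section 8.4 strata by IGA score at 4 weeks. For an overwritten infant, the withdrawal examination supplies both the stratum and the Last Visit outcome analysed within it.

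The trial is uncontrolled and its primary result is a single proportion with a confidence interval, so a misassigned record goes straight into the estimate.

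**Working it through.** **Does the exclusion reach withdrawal data?** Section 3.4 names unscheduled data and withdrawal data as two categories in one sentence. The exclusion in the next sentence is worded for unscheduled data only, so withdrawal data stay in.

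**How long is the exposed interval?** Let d be the day of the Week 4 examination. The days open to overwriting are 42 − d:

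| d | 42 − d |
|---|---|
| 22 | 20 |
| 28 | 14 |
| 29 | 13 |
| 35 | 7 |

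The nominal Week 4 day is not stated. Placing visits at 7 × week reproduces 14 of the 14 upper limits in Table 3.4-1 from Week 1 to Week 48 if a midpoint day goes to the earlier visit. Placing them at 7 × week + 1 reproduces 13 of 14 if it goes to the later visit; only Week 1 fails. Day 28 and Day 29 are therefore both shown.

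**In which direction can status change?** Section 3.3 admits infants "younger than 2 years of age with AD and an IGA score of 2 or 3". Response requires IGA 0 or 1 with a fall of at least 2 grades.

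- *Dose raised under the IGA criterion.* The Week 4 IGA is 2, 3 or 4. With baseline 2 or 3, that gives 6 combinations, all non-response. A later score can only leave this unchanged or turn it into a response (IGA 0 from baseline 2; IGA 0 or 1 from baseline 3). These overwrites can only raise the rate.
- *Responder who worsens and withdraws.* For example, baseline 3, IGA 1 on Day 29 and IGA 3 at withdrawal on Day 38 turns a responder into a non-responder. These overwrites can only lower the rate.

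**How much does one change matter?** The shift is 1/N. N is assumed, because the public copy shows none:

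- N = 20: 1/20 = 5.0 percentage points
- N = 40: 1/40 = 2.5
- N = 60: 1/60 = 1.7

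Clopper-Pearson 95% intervals at an assumed N of 40, starting from an assumed 20 responders:

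| Responders | Rate | 95% interval |
|---|---|---|
| 19/40 (one change down) | 47.5% | 31.5 to 63.9 |
| 20/40 | 50.0% | 33.8 to 66.2 |
| 21/40 (one change up) | 52.5% | 36.1 to 68.5 |
| 23/40 (three changes, all up) | 57.5% | 40.9 to 73.0 |

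The last row illustrates scale only. Opposite changes cancel, and the documents give no withdrawal rate for this interval.

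**Secondary wording point.** The notes to Figure 3-1 describe the visit 2 weeks after a first 1% dose as scheduled, whereas the exclusion in section 3.4 speaks of unscheduled data. If 1% starts on Day 28, that visit falls on Day 28 + 14 = 42, inside the Week 4 window. If it starts on Day 29, the visit falls on Day 43, outside. The label therefore affects the Week 4 record only when 1% starts by Day 28.

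**The case against.** The strongest counter-argument is in section 3.4 itself. For an infant whose dose is raised at Week 4, it equates the Week 4 record with the record at the time of increase, and Table 3.4-2 ties that to the day the increase was first directed. A Day 40 withdrawal record cannot satisfy this, so the authors probably had the Week 4 examination in mind. That is fair evidence of intent. It does not repair the rule, because the dose-increase time points "will also be defined in addition to the above-described time points in analysis" and leave the Table 3.4-1 selection as it is. The two statements then conflict.

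Other objections stand in part:

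- The path in the example is narrow. It needs a dose increase, improvement within 11 days and withdrawal by Day 42, while section 3.2.2.3 allows interruption instead of withdrawal. Few infants are likely to be affected, and many overwrites would leave status unchanged.
- Section 3.2.2.1 also permits an increase at IGA below 2, where an overwrite on 1% can lower the rate. The one-way statement holds only for increases under the IGA criterion.
- For an infant still on 0.3%, taking the last value in the window is a recognised convention. The conflict there is only with the end of the primary assessment part, and it is weaker than for an infant on 1%.
- Using data on either formulation could be a deliberate choice. That would settle which data count at a time point. It does not explain replacing an observed Week 4 examination with a later one. The section 8 qualifier about exceptions does not help, since section 8.1 states none.
- An infant whose last examination is the Week 4 examination has the same record for stratum and Last Visit under any rule. The subgroup point is therefore minor; what the overwrite adds is a stratum that is no longer the score at the Week 4 examination.
- Section 8.1 is estimation only and shows no threshold, so no visible conclusion turns on one infant.

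**Conclusion.** The concern holds. As written, section 3.4 lets a non-missing withdrawal IGA after the Week 4 examination and by Day 42 replace the primary record, and it can count a result on 1% as a Week 4 response to 0.3%. This contradicts the primary objective and the plan's own definition of the primary assessment part.

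The effect is 1/N per changed infant, between 1.7 and 5.0 percentage points for an assumed N of 60 down to 20. The net direction is mixed and the total effect cannot be estimated from the documents. It should be fixed because it concerns the primary endpoint and the repair is cheap, not because a large bias is expected. The unclear wording of the exclusion is a lesser matter, and the conclusion does not depend on it.

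**What to change.** In section 3.4, add an order of precedence for the Week 4 efficacy value:

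1. The non-missing value from the Week 4 examination, if there is one in Day 22 to 42.
2. Otherwise, the last non-missing value in Day 22 to 42 obtained before any application of 1%, including a withdrawal examination.
3. If neither exists, the missing-data rule in section 3.5.1 applies and the infant is a non-responder.

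In the same edit, name the visit 2 weeks after a first 1% dose explicitly in the exclusion, however it is recorded, and state which visits bound the 4-to-8-week interval.

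The cost is two or three sentences in the SAP and one programming condition for the Week 4 record. No new data are needed, and nothing changes in how infants are treated.
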